APPENDIX M. PUBLICATION POLICY

All unpublished information given to the investigator by the sponsor shall not be published or disclosed to a third party without the prior written consent of the sponsor.

The results of this study may be published or presented at scientific meetings. If this is foreseen, the investigator agrees to submit all manuscripts or abstracts to the sponsor before submission. This allows the sponsor to protect proprietary information and to provide comments.

The sponsor will comply with the requirements for publication of study results: “Recommendations for the Conduct, Reporting, Editing, and Publication of Scholarly Work in Medical Journals” (www.ICMJE.org). Publication of the results will occur in a timely manner according to applicable regulations. In accordance with standard editorial and ethical practice, the sponsor will generally support publication of multicenter studies only in their entirety and not as individual investigational center data. In this case, a coordinating investigator will be designated by mutual agreement.

Authorship will be determined by mutual agreement and in line with International Committee of Medical Journal Editors authorship requirements:

- substantial contributions to the conception or design of the work; or the acquisition, analysis, or interpretation of data for the work
- drafting the work or revising it critically for important intellectual content
- final approval of the version to be published
- agreement to be accountable for all aspects of the work in ensuring that questions related to the accuracy or integrity of any part of the work are appropriately investigated and resolved

The publications committee established by the sponsor will oversee this process. Additional publications may follow. Policies regarding the publication of the study results are defined in the financial agreement.

No patent applications based on the results of the study may be made by the investigator, nor may assistance be given to any third party to make such an application without the written authorization of the sponsor.

APPENDIX N. CLINICAL LABORATORY TESTS

Table 7 provides the clinical laboratory assessments to be performed in the study.

Table 7: Clinical Laboratory Tests

Serum Chemistry	Hematology and Coagulation	Urinalysis
Calcium	Hemoglobin	Protein
Phosphate	Hematocrit	Glucose
Sodium	Erythrocytes	Ketones
Potassium	Platelets	Hemoglobin
Chloride	Leucocytes	pH
Creatinine	– Neutrophils	Specific gravity
Glucose	– Lymphocytes	Microscopic tests
BUN	– Eosinophils	– Bacteria
LDL	– Monocytes	– Erythrocytes
HDL	– Basophils	– Leucocytes
Triglycerides	Lymphocytes atypical	– Crystals
Urate	Prothrombin INR	– Casts
ALT		
AST		
LDH		
GGT		
Alkaline phosphatase		
Bicarbonate		
Carbon dioxide		
Protein		
Albumin		
Bilirubin		
Direct bilirubin		

ALT = alanine aminotransferase; AST = aspartate aminotransferase; BUN = blood urea nitrogen; GGT = gamma glutamyl transpeptidase; HDL = high density lipoprotein; INR = International Normalized Ratio; LDH = lactate dehydrogenase; LDL = low density lipoprotein.

APPENDIX O. INJECTION INSTRUCTIONS

[figure not shown]
Patient Education

Clinical Center
NATIONAL INSTITUTES OF HEALTH

Giving a subcutaneous injection

What is a subcutaneous injection?

A subcutaneous injection is given in the fatty layer of tissue just under the skin.

A subcutaneous injection into the fatty layer of tissue (pinched up to give the injection) under the skin.

Why are subcutaneous injections given?

These injections are given because there is little blood flow to fatty tissue, and the injected medication is generally absorbed more slowly, sometimes over 24 hours. Some medications that can be injected subcutaneously are growth hormone, insulin, epinephrine, and other substances.

Preparing to give medication

Subcutaneous injections are not given if the skin is burned, hardened, inflamed, swollen, or damaged by a previous injection.

1. Wash your hands thoroughly. This is the best way to prevent infection.

2. Assemble your equipment:

Medication

- May be a multidose vial of liquid or may be a vial with powder that requires "reconstitution." Follow the manufacturer's instructions as to what and how much diluent to use. The diluent is usually saline (a mixture of salt water) or sterile water.

Syringe or pen and needle

Depending on the amount of medication to be given and the size of the child or adult:

- 0.5 cc, 1.0 cc, or 2 cc with 27-gauge needle (5/8 of an inch long)
- 3-cc luer lock syringe—used when solution is more than 1 cc
- 25-gauge needle (5/8 of an inch long or 27-gauge needle (5/8 of an inch long)
- 0.3 mL insulin syringes with 31-gauge needles (3/16 to 5/16 inches long) are available for those who are visually impaired or for those who need very small doses of medication.
- medication log
- container for syringe disposal
- sterile 2 x 2-inch gauze pad
- alcohol pads

Drawing up medication

1. Check the label for correct medication.
2. Remove the soft metal or plastic cap protecting the rubber stopper of the vial.
3. If the medication vial or pen can be used for more than one dose, record the date and time on the label.

4. Clean the exposed rubber stopper using an alcohol swab.
5. Remove the syringe from the plastic or paper cover. If necessary, attach the needle securely.
6. Pull back and forth on the plunger by grasping the plunger handle. Grasping the handle end will prevent contamination of the plunger shaft (which is sterile).
7. With the needle capped, pull back the plunger, filling the syringe with air equal to the amount of medication to be administered.
8. Remove the cap covering the needle and set it on its side to prevent contamination. Be careful not to touch the needle. The inside of the cap and needle is sterile, and the needle will be covered again with this cap.
9. With the vial in an up-right position, push the needle through the cleansed rubber stopper on the vial. Push the needle in at a 90 degree angle, being careful not to bend the needle.
10. Inject the air in the syringe into the vial. Air is injected into a multi-dose vial to prevent a vacuum from forming. If too little or no air is injected, withdrawing the medication may be difficult. If too much air is injected, the plunger may be forced out of the barrel causing the medication to spill.
11. Turn the vial upside down, with the needle remaining in the vial. The needle will be pointing upward.
12. Make sure that the tip of the needle is completely covered by the medication. This will make it easier to withdraw the solution (and not air).
13. Pull back on the plunger to fill the

syringe with the correct dose of medication.

14. Keep the vial upside down, with the needle in the vial pointed upward. Tap the syringe, or “flick” it with your fingertips. This helps move bubbles to the top of the syringe.
15. Once the bubbles are at the top of the syringe, gently push on the plunger to force the bubbles out of the syringe and back into the vial.

Or, you may push all the medication solution back into the vial, withdraw again slowly, and repeat steps 14 and 15.

Note: It is important to eliminate large air bubbles because they take up space needed for the medication, and they may cause pain or discomfort when injected.

16. After removing the bubbles, check the dose of medication in the syringe to be sure you have drawn up the correct amount.

[figure not shown]
If using a pen, skip steps 5 to 16. Do the following:

- a. Attach needle to pen by cleaning the top with alcohol and screwing on the needle.
 - b. Dial in your prime volume (usually 0.02 mL) using the manufacturer’s directions.
 - c. With pen needle pointed up, push the injection button completely. You should see a drop or stream of liquid. If you do not, repeat priming steps until this occurs.
 - d. Dial in prescribed dose of medication.
17. After the medication is correctly drawn up, carefully replace the needle cap to prevent contamination.

[figure not shown]
Locating injection sites

Subcutaneous injections can be given in the arms, legs, or abdomen. Your nurse or doctor will help you select the best sites to administer your medication.

1. To locate injection sites on the arms, fold one arm across the chest. Place your hand on the shoulder and draw an imaginary line below your hand. Place another hand on the elbow. Draw an imaginary line down the outer side of the arm and down the center front of the arm, starting at the elbow. The area inside these imaginary lines is where injections are given. (If you are injecting imagine the hand placement.)

[figure not shown]

Injection sites on the side of the arm.

Injection sites on the back of the arm.

[figure not shown]
2. To locate injection sites on the thighs, sit down, place your hand above the knee, and draw an imaginary line above it. Place your hand at the uppermost part of the thigh and draw an imaginary line below your hand. Draw an imaginary line down the outer side of the leg and down the center front of the leg. The area within these imaginary lines is where injections may be given.
3. To locate injection sites on the abdomen, place your hands on the lower ribs and draw an imaginary line them. Use this area below your hands for injections, as far around as you can pinch up fatty tissue. use a 1-inch area around the navel.

Injection sites on the front of the thigh.

Rotating injection sites

It is extremely important to rotate sites to keep the skin healthy. Repeated injections in the same spot can cause scarring and hardening of fatty tissue that will interfere with absorption of medication. Each injection should be about 1 inch apart. Each injection site can be measured with a small dot Band-Aid, providing the patient is not sensitive to the adhesive. Start injections at the highest point of the area and continue down toward the point farthest away from the body (for example, upper arm down toward elbow). It is preferable to use all sites available on one body part (arm or leg) before moving on to another. However, some parents find that children are more accepting of injections if they are rotated from one body part to another (arm, leg, arm, leg). Avoid giving injections in areas that are burned, reddened, inflamed, swollen, or damaged by prior injections.

Injection sites on the abdomen

Preparing the skin

Since the skin is the body's first defense against infection, it must be cleansed thoroughly before a needle is inserted.

Cleanse the skin with a back-and-forth motion using an alcohol swab. This motion moves bacteria away from the injection site. Allow the alcohol to dry completely by air.

Giving the injection

1. Take the cover off the needle. Be careful not to contaminate the needle. Place the cover on its side.
2. Hold the syringe in one hand like pencil or a dart.
3. Grasp the skin between the thumb and index finger with your other hand and pinch up.
4. Quickly thrust the needle all the way into the skin. Do not "push" the needle into the skin slowly or thrust the needle into the skin with great force.

Do not press down on the top of the plunger while piercing the skin.

5. Insert the needle at a 90-degree (right) angle. This angle is important to ensure that the medications will be injected into the fatty tissue. However, for small children, and persons with little subcutaneous fat on thin skin, you may be taught to use a 45-degree angle.

If using a pen, insert the pen needle at a 90-degree angle.

6. After the needle is completely inserted into the skin, release the skin that you are grasping.

Press down on the plunger to release medication into the subcutaneous layer in a slow, steady pace.

If using a pen, press the injection button completely (or until it clicks). Count 10 seconds before removing the needle from the skin.

7. As the needle is pulled out of the skin, gently press a 2 x 2 gauze onto the needle insertion site. Pressure over the site while removing the needle prevents skin from pulling back, which may be uncomfortable. The gauze also helps seal the punctured tissue and prevents leakage.
8. If instructed to do so, press or rub the site for a few seconds.
9. It is not serious if you notice blood at the site after the needle is removed. You may have nicked a surface blood vessel when you injected, and blood is following the needle track out to the surface. Simply press the site with a 2 x 2

gauze pad. Also, a small amount of clear fluid may appear at the site. This may be medication that is following the needle track to the surface. Again, apply pressure using a 2 x 2 gauze pad.

If using a pen:

Untwist needle on the pen and safely dispose the needle. Replace pen cap and store as instructed.

Safe needle disposal

Please refer to the Clinical Center pamphlet "Handling Sharp Objects Safely at Home."

- o Place the syringe or needle in a hard plastic or metal container with a tightly secured lid.
- o Do not re-cap needles after use. Keep the container out of the reach of children or pets.
- o When the container is three-quarters full, take it to a health care facility (hospital or doctor's office) for proper disposal. If you live within driving distance of NIH, you can bring your container to NIH for proper disposal.

Medication
Dose
Schedule
Primary Nurse
Phone
Physician
Phone

This information is prepared specifically for persons taking part in clinical research at the National Institutes of Health Clinical Center and may not apply to patients elsewhere. If you have questions about the information presented here, talk to a member of your health care team.

Products/resources named serve as examples and do not imply endorsement by NIH. The fact that a certain product/resource is not named does not imply that such product/resource is unsatisfactory.

National Institutes of Health Clinical Center
Bethesda, MD 20892

Questions about the Clinical Center?
<http://www.cc.nih.gov/comments.shtml>

6/2012

NIH...Turning Discovery Into Health

APPENDIX P. MANAGEMENT OF STUDY ACTIVITIES DURING COVID-19

This appendix is to address the modifications in study conduct during the Coronavirus disease 2019 (COVID-19) pandemic.

The changes specified in this appendix will be effective for the duration of the COVID-19 pandemic. Once the pandemic resolves and centers/countries are able to resume normal functioning, this appendix will become void.

The following sections are affected:

Section 3.5 Schedule of Study Procedures and Assessments (Table 4)

Home visits are permitted for patients who are not able to go to the investigational center for their visit(s) or if the investigational center staff are not able to see patients at the investigational center due to the COVID-19 pandemic. Home visits must be completed by the principal investigator or a subinvestigator and may also include trained study staff (ie, a medically qualified person designated by the investigator or a home care service provider for certain assessments), as required, to complete all visit assessments/procedures.

Visits should be conducted in accordance with the timelines specified in the protocol (see [Table 4](#)).

Appendix D. Ethics

For home visits, a verbal consent process will be applied for each patient prior to the home visit and will follow written informed consent as per local regulations before any study procedures or assessments are performed.

**LIST OF ABBREVIATIONS AND DEFINITIONS OF TERMS**

Abbreviation	Term
AE	adverse event
ANCOVA	analysis of covariance
ANOVA	analysis of variance
BMI	body mass index
CGI-S	Clinical Global Impression-Severity
CI	confidence interval
CM	chronic migraine
COVID-19	Coronavirus disease 2019
CRF	case report form
DSM-V	Fifth Edition of the Diagnostic and Statistical Manual of Mental Disorders
eC-SSRS	electronic Columbia-Suicide Severity Rating Scale
ECG	electrocardiogram
EM	episodic migraine
EOT	end of treatment
FSH	follicle-stimulating hormone
HAM-A	Hamilton Anxiety Scale
HAM-D 17	Hamilton Depression Rating Scale-17 items
HIT-6	6-item Headache Impact Test
ICHD-3	International Classification of Headache Disorders, 3rd revision
IMP	investigational medicinal product
IRT	interactive response technology
ITT	intent-to-treat
LS	least square
MDD	major depressive disorder
MedDRA	Medical Dictionary for Regulatory Activities
MI	multiple imputation
mITT	modified intent-to-treat
MMRM	mixed-effects model repeated measures
MSQoL	Migraine-Specific Quality of Life
NSAID	non-steroidal anti-inflammatory drug
PANSS	Positive and Negative Syndrome Scale

Statistical Analysis Plan

Abbreviation	Term
PHQ-9	Patient Health Questionnaire-9
PP	per-protocol
PT	preferred term
R&D	Research and Development
SAP	statistical analysis plan
SD	standard deviation
SE	standard error
SI	standard international
SOC	system organ class
SOP	Standard Operating Procedure
sc	subcutaneous
WHO	World Health Organization
WPAI:GH	Work Productivity and Activity Impairment Questionnaire General Health

## INTRODUCTION

This Statistical Analysis Plan (SAP) describes the planned analysis and reporting for Teva Branded Pharmaceutical Products Research and Development (R&D), Inc. study TV48125-MH-40142 (A Multicenter, Randomized, Double-Blind, Placebo-Controlled, Parallel-Group Study Followed by an Open-Label Extension to Evaluate the Efficacy and Safety of Fremanezumab for Preventive Treatment of Migraine in Patients with Major Depressive Disorder), and was written in accordance with Standard Operating Procedure (SOP) GSD\_SOP\_702 (SAP).

The reader of this SAP is encouraged to read the study protocol for details on the conduct of this study, the operational aspects of clinical assessments, and the timing for completing the participation of a patient in this study.

The SAP is intended to be in agreement with the protocol, especially with regards to the primary and all secondary endpoints and their respective analyses. However, the SAP may contain more details regarding these particular points of interest, or other types of analyses (e.g. other endpoints). When differences exist in descriptions or explanations provided in the study protocol and this SAP, the SAP prevails; the differences will be explained in the Clinical Study Report.

# 1. STUDY OBJECTIVES AND ENDPOINTS

## 1.1. Primary and Secondary Study Objectives and Endpoints

The primary and secondary study objectives and endpoints are in [Table 1](#):

**Table 1: Primary and Secondary Study Objectives and Endpoints**

Objectives	Endpoints

Primary objective: To evaluate the efficacy of monthly 225 mg subcutaneous (sc) fremanezumab in adult patients with migraine and major depressive disorder (MDD)
	
Mean change in the monthly average number of migraine days from the 28-day baseline period during the 12-week period after the first dose of study drug

Key secondary objective: To evaluate the efficacy of monthly 225 mg sc of fremanezumab in adult patients with migraine and MDD on the reduction of MDD symptoms
	
Mean change in depression symptoms from randomization (day 1) to week 8 after the first dose of study drug as measured by:
 
 
• Hamilton Depression Rating Scale-17 items (HAM-D 17)
 

Secondary objective: To evaluate the efficacy of monthly 225 mg sc fremanezumab in adult patients with migraine and MDD in terms of responder rates in monthly migraine days
	
Number of patients with 50% or more reduction from the 28-day baseline period in the monthly average number of migraine days during 12 weeks after the first dose of study drug

Secondary objective: To evaluate the efficacy of monthly 225 mg sc fremanezumab in adult patients with migraine and MDD in terms of improving quality of life
	
Mean change in quality of life from randomization visit (day 1) to week 12 after the first dose of study drug as measured by:
 
 
• Migraine-Specific Quality of Life (MSQoL) questionnaire, role function-restrictive and role function-preventive domains
 

Fremanezumab at monthly doses of 225 mg sc, and placebo alternatively, in the 12-week double-blind treatment period

**4. Intercurrent events strategy:**

- a. Early discontinuation due to lack of efficacy: hypothetical strategy
- b. Early discontinuation due to adverse event: hypothetical strategy
- c. Initiation of prohibited therapy: hypothetical strategy
- d. Impact of COVID-19: hypothetical strategy

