4.3. Withdrawal Criteria and Procedures for the Patient

Each patient is free to withdraw from the study or discontinue from IMP at any time, without prejudice to their continued care. Patients must be withdrawn from the IMP if any of the following events occur:

1. Patient withdraws consent or requests discontinuation from the IMP or withdrawal from the study for any reason.
2. Patient develops an illness that would interfere with his/her continued participation.
3. Patient is noncompliant with the study procedures and assessments or administration of IMPs in the opinion of the investigator.
4. Patient takes prohibited concomitant medications or receives prohibited therapies as defined in this protocol.
5. A female patient has a confirmation of pregnancy during the study from a positive urine pregnancy test.
6. The sponsor requests withdrawal of the patient.
7. Patient experiences an adverse event or other medical condition that indicates to the investigator that continued participation is not in the best interest of the patient.

Patients should be treated with standard of care after withdrawal from or termination of the study as appropriate.

Investigators should attempt to obtain information on patients in the case of withdrawal from the study or discontinuation from IMP. Results of any evaluations and observations, together with a narrative describing the reason(s) for withdrawal from the study or discontinuation from IMP, must be recorded in the source documents. The electronic case report form (eCRF) must document the primary reason for withdrawal from the study or discontinuation from IMP.

See [Appendix F](#) for information regarding how the study will define and address lost to follow-up patients to help limit the amount and impact of missing data.

If the reason for withdrawal from the study or discontinuation from IMP is an adverse event and/or clinically significant abnormal laboratory test result, monitoring will be continued as applicable (eg, until the event has resolved or stabilized, until the patient is referred to the care of a health care professional, or until a determination of a cause unrelated to the IMP or study procedure is made). The specific event or test result (including repeated test results, as applicable) must be recorded on both the source documentation and the eCRF; both the adverse events page and the relevant page of the eCRF will be completed at that time.

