9.2. Analysis Sets

9.2.1. Intent-to-Treat Analysis Set

The intent-to-treat (ITT) analysis set will include all randomized patients.

In the ITT analysis set, treatment will be assigned based on the treatment to which patients were randomized, regardless of which treatment they actually received.

Data collected from patients after treatment discontinuation will be included in the ITT analysis set.

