## **2.4. Sample Size and Power Considerations**

A sample size of 288 (144 per treatment group) evaluable patients completing the study will provide 90% power to detect a treatment difference of 2 days with a common standard deviation of 5.2 days in changes from the 28-day baseline period in monthly average migraine days between active and placebo groups at a 2-sided alpha level of 0.05. This sample size will provide approximately 80% power to detect a treatment difference of 2 points with a common standard deviation of 6 points in the change from randomization visit (day 1) in HAM-D 17 total score at a 2-sided alpha level of 0.05. Assuming a 15% drop-out rate, approximately 340 patients (approximately 170 patients per treatment group) will be randomized.

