## 6. EFFICACY ANALYSIS

### 6.1. General

Migraine days will be defined as follows. If the headache fulfills the criteria for migraine on any given day, the consecutive days are part of the same migraine attack and are therefore considered to be migraine days as well (even if they do not fulfill the criteria for migraine). These days only reflect normal fluctuations in migraine severity that lead to or represent the resolution of a full-blown migraine attack. Accordingly, for the purpose of this study, a migraine day is endorsed when at least one of the following situations occurs:

- a calendar day (00:00 to 23:59) demonstrating at least 4 consecutive hours of a headache meeting the criteria for migraine with or without aura
- a calendar day (00:00 to 23:59) demonstrating at least 4 consecutive hours of a headache meeting the criteria for probable migraine, a migraine subtype where only 1 migraine criterion is missing
- a calendar day (00:00 to 23:59) demonstrating a headache of any duration that was treated with migraine-specific medications (triptans and ergot compounds)
- a calendar day (00:00 to 23:59) that is immediately consecutive (happening 1 day before or 1 day after) of any day fulfilling any of the 3 criteria above, where individuals report headache of any duration

The **monthly average number of days or hours** of efficacy variables (migraine days) **during the 12-week period** after the 1st dose of study drug will be derived and normalized to **28** days equivalent using the following formula.

$$\frac{\sum \text{Days or hours of efficacy variable over the 12 week period}}{\sum \text{Days with assessments recorded in the eDiary for the 12 week period}} \times 28 \quad (1)$$

The **monthly number of days or hours** of efficacy variables **during a 4-week period** after each dose will be derived and normalized to **28** days equivalent using the following formula, where monthly data separated by each visit of study drug dosing will be used.

$$\frac{\sum \text{Days or hours of efficacy variable during the 4 week period}}{\sum \text{Days with assessments recorded in the eDiary for the 4 week period}} \times 28 \quad (2)$$

The **baseline values** will be calculated using all data collected in the run-in period.

$$\frac{\sum \text{Days or hours of efficacy variable during the run – in period}}{\sum \text{Days with assessments recorded in the eDiary for the run – in period}} \times 28 \quad (3)$$

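### The primary estimand treats prohibited therapy, COVID-19 and two kinds of discontinuation hypothetically, but the visible SAP counts every recorded diary day, including any recorded after these events

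*SAP*

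**What the plan says.** SAP 1.3 lists four intercurrent events: early discontinuation for lack of efficacy, early discontinuation for an adverse event, start of prohibited therapy ("Initiation of prohibited therapy: hypothetical strategy") and the impact of COVID-19. All four get a hypothetical strategy.

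Formula (1) in SAP 6.1 gives the primary variable: migraine days over the 12 weeks, divided by "Days with assessments recorded in the eDiary for the 12 week period", times 28. Formula (2) does the same for each month. SAP 4.3 adds only that at least 10 diary days are needed for proration. The analysis uses the mITT set (SAP 6.1). Under SAP 3.1.3, patients who begin prohibited therapy are left out of the per-protocol set; no similar exclusion is stated for mITT.

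The protocol is not uniform on what follows an event:

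- Section 4.3 opens its list, which includes taking prohibited medication, with "Patients must be withdrawn from the IMP if any of the following events occur". A later paragraph of 4.3 treats the need for a prohibited medication as requiring discontinuation of the patient.
- Section 9.7 has patients who begin prohibited therapies leave the study.
- Appendix C names prohibited medication as a possible important deviation and lets the sponsor keep such a patient in the study.
- Section 9.2.1 says: "Data collected from patients after treatment discontinuation will be included in the ITT analysis set".
- The notes to Table 4 run the diary through the end-of-treatment or early withdrawal visit.

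**The concern.** A hypothetical strategy asks what the outcome would have been had the event not happened. Days recorded after the event do not answer that question unless they are set aside or replaced under a stated assumption. Formula (1) does neither, so recorded post-event days are handled as a treatment-policy strategy would handle them.

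What is at stake is first the meaning of the headline estimate: it would carry an estimand label that its derivation does not deliver. Second, there is a possible bias. If more placebo than fremanezumab patients start another effective therapy, their improved days are credited to placebo and the difference shrinks. An excess in the active arm would work the other way. For COVID-19 the direction cannot be stated, because the affected days are not defined.

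**Working it through.** **1. The plan's own figure.** SAP 2.4 claims that its planned size "will provide 90% power to detect a treatment difference of 2 days with a common standard deviation of 5.2 days". The evaluable number there is 288, or 144 per arm, and the test is two-sided at 0.05. Power is approximately Φ(δ / (SD × √(2/n)) − 1.96).

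- Standard error = 5.2 × √(2/144) = 0.613.
- At δ = 2: 2/0.613 = 3.26, and Φ(3.26 − 1.96) = 0.904 (0.902 with the noncentral t).
- The formula needs 143 per arm, against 144 stated.
- "Assuming a 15% drop-out rate, approximately 340 patients": 288/0.85 = 339.

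The sample size reproduces, so this is not a sample-size error.

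**2. When the formula departs from the target.** Take an assumed patient with 56 days at 12 migraine days per 28, then 28 days on prohibited therapy at 6 per 28.

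- As written: (24 + 6)/84 × 28 = 10.0.
- Post-event days set aside: 24/56 × 28 = 12.0.
- If the patient leaves at day 56 and records nothing more: 24/56 × 28 = 12.0, the same as the set-aside value.

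The mismatch exists only where post-event days are recorded.

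**3. Can such days exist?**

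- *Prohibited therapy:* yes. Medication use is asked about at visits (protocol 5.7), and the double-blind visits are 28 days apart (Table 4). A therapy started just after a visit could run for about 28 of 84 days (33%) before the next inquiry. Appendix C also allows continuation.
- *COVID-19:* the visible SAP mentions it only in the abbreviation list and the estimand, with no definition or data rule.
- *Stopping study drug for the two listed reasons:* possible if stopping drug and leaving the study are separate. Protocol 9.2.1 foresees data after treatment discontinuation.

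**4. Do the other analyses close the gap?** No.

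- The MMRM (SAP 6.2.3.1) uses formula (2) and so the same recorded days.
- The multiple imputation (6.2.3.2) keeps observed days and imputes only missing ones. It imputes fremanezumab terminations for adverse event or lack of efficacy from placebo data, which is a different assumption from the event not having occurred.
- The per-protocol repeat drops prohibited-therapy users altogether.

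**5. Size, on assumed inputs.** The documents give no event rates. Let f be the excess share of placebo patients with an event, s the share of their counted days that fall after it, and g the reduction on those days in migraine days per 28. The expected difference is then 2 − f × s × g.

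| f | s | g | Difference (days) | Power, 144 per arm |
|---|---|---|---|---|
| 15% | 5% | 4 | 1.97 | 89.5% |
| 5% | 17% | 2 | 1.98 | 89.9% |
| 10% | 33% | 4 | 1.87 | 86.2% |
| 15% | 50% | 4 | 1.70 | 79.2% |

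The first row represents prompt withdrawal. The last is a stress case: it needs 42 of 84 days on prohibited therapy with the diary continuing, which the withdrawal provisions make hard to reach.

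**The case against.** The strongest reply is that patients with these events leave. The diary stops at the early withdrawal visit, Table 4 has no schedule for patients off drug but still in the study, and 4.3 (later paragraph) and 9.7 call for discontinuation. With no later days, formula (1) prorates pre-event days only, which is an implicit hypothetical approach. This stands for discontinuation that ends participation. A reader might infer that the whole primary analysis is a treatment-policy analysis, or that every discontinuation breaks the estimand; the documents do not support either. The reply does not cover days before the patient leaves, patients allowed to continue, or COVID-19.

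The sentence in protocol 9.2.1 concerns the ITT set. SAP 3.1.1 does not repeat it, the SAP primary uses mITT, and the SAP prevails over the protocol. So it does not by itself establish what the primary analysis does. Nor does its absence from the SAP create an exclusion.

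The power figures use 144 completers per arm, while mITT could approach 170. At 1.87 days and 170 per arm, the standard error is 5.2 × √(2/170) = 0.564, and Φ(1.87/0.564 − 1.96) is about 0.91. A reader might infer a material loss of power; the documents do not show one.

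Finally, estimand items 1 to 3 and SAP Appendices A and B, the latter listed in the contents as covering endpoint derivation, are not in the supplied text. A cut-off rule may be there.

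**Conclusion.** The point holds within limits. In the visible SAP the hypothetical strategy is not carried into formulas (1) and (2), so any diary days recorded after a listed event count in the primary analysis. The gap covers prohibited-therapy days while the patient is still in the study, COVID-19-affected days, and any days after stopping study drug for lack of efficacy or an adverse event.

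The numerical effect is probably small. It rests wholly on assumed rates, with the excess of events taken to be in the placebo arm; in that case it dilutes the difference and does not inflate it. The firmer reason to act is that the estimate and its label should agree. The conclusion depends on the sponsor confirming that the appendices and estimand items not supplied contain no such rule.

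**What to change.** In SAP 4.3 and 6.1, state that formulas (1) and (2) use, in numerator and denominator, only diary days before the start of prohibited therapy or before study-drug discontinuation for lack of efficacy or an adverse event. Define the discontinuation date, which is not self-evident with injections at days 1, 29 and 57. Do not extend the cut-off to other reasons for discontinuation, since SAP 1.3 does not list them. Say whether the 10-day minimum applies to the days that remain.

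Define COVID-19 impact and apply the same rule to it. Report the all-days version as a supplementary treatment-policy analysis. Alternatively, relabel the strategy in SAP 1.3 for any event whose later days are to be kept.

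Protocol 4.3 (both statements), 9.2.1, 9.7 and Appendix C must be reconciled on what happens to a patient, and to that patient's data, after prohibited therapy or stopping study drug. Which conduct rule applies is for the sponsor to settle.

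The cost is SAP wording and an event date for each affected patient in the derivation. A few diary days are lost from the primary analysis.
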